	HRA REC Scoping interviews with referral organisations and setting up referral pathways	Recruitment for scoping interviews and subsequent engagement	Successful engagement with all major local referral organisations for both issues	Engagement with some but not all of major local referral organisations for both issues	opinion Failure to engage with at least one appropriate referral organisation for each issue	
	Views of intervention from participants in lay focus groups and co- production workshops	Lay focus groups and co-production workshops	Favourable view towards intervention from all participants in lay focus groups and co-production workshops	Mixed views as to suitability of the intervention	Majority view not in support of the intervention	
	Development of all aspects of the intervention	Co-production workshops and modelling	Successful development of all 7 aspects of the intervention	Partial failure to develop any one aspect of the intervention	Failure to develop any one aspect of the intervention	
5	Recruitment of pharmacies (control and intervention) across rural/urban, small pharmacy / commercial store	Recruitment of pharmacies	Recruitment of 3 pharmacies per category: a. urban/large commercial b. urban/small pharmacy c. rural/large commercial d. rural/small pharmacy	Failure to recruit at least one pharmacy for any of these categories	Failure to recruit any pharmacies	
	Randomisation procedures - are pharmacies willing to be allocated to the control group	Randomisation	All 12 agree to be randomised	At least one pharmacy was not willing or able to be randomised	None of them were willing or able to be randomised	
,	Recruitment of staff within pharmacies (3 per pharmacy, of whom one should be a pharmacist)	Staff recruitment	Recruitment of at least 2 per pharmacy	Recruitment of 1 per pharmacy	None recruited	
3	Ability to deliver training to all staff (2 sessions, 24 staff)		All 24 intervention staff attended and training delivered	Staff from half of the pharmacies attended training	Failure to train anyone in a particular pharmacy	
9	Assessment of change in behavioral intention after training – CPD Reaction Questionnaire	CPD Questionnaire and feedback	All staff completed the questionnaire with positive indication of feeling adequately trained to undertake the intervention	50% completed, and or results show 50% of staff do not feel adequately trained to undertake the intervention	0% completed and / or all staff feel unprepared	

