24	Client basic demographic data collected in consultation	Data sheets in pharmacies	Staff able to complete at least 80% of the data for at least 80% of the clients	Failure to record at least 50% of the data for at least 50% of the clients	Failure to record at least 30% of the data for at least 30% of the clients	
25	Willingness to be followed up	Data sheets in pharmacies	Staff able to complete at least 80% of the data for at least 80% of the clients	Failure to record at least 50% of the data for at least 50% of the clients	Failure to record at least 30% of the data for at least 30% of the clients	
26	Pharmacy business data - prescription and service items. These data will be collected at the beginning of the study retrospectively for the 6 months prior, and during the 6 months of the implementation (for both control and intervention)	Pharmacy companies	Able to collect at least 90% of the data from 90% of the intervention pharmacies		Failure to collect at least 50% of the data from 50% of the intervention pharmacies, or an indication from this data that the intervention is having a deleterious effect on the business and staff wellbeing in any one of the pharmacies.	
27	Control pharmacies – number of queries for SI or DA, and if any Ask for ANI / safe space requests	Pharmacy companies	Able to collect at least 80% of the data from all 4 intervention pharmacies		Failure to collect 50% of the data from any one of the intervention pharmacies	
28	Community survey responses	Community survey	Completion of 600 full responses to community survey within the time period	Completion of 400 full responses to community survey within the time period	Completion of 300 or less full responses to community survey within the time period	
29	Acceptability and effectiveness of training using the Theoretical Framework for Acceptability of Healthcare Interventions – in staff focus groups	Staff focus Groups	All staff reporting that the training and ongoing support had sufficiently prepared them for completed the undertaking the intervention	Four or more staff reporting that the training and ongoing support had not sufficiently prepared them for completed the undertaking the intervention	Half or more of all staff (12/24) reporting that the training and ongoing support had not sufficiently prepared them for completed the undertaking the intervention	

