30	Acceptability and effectiveness of intervention using the Theoretical Framework for Acceptability of Healthcare Interventions - in staff focus groups	Staff focus groups	All staff reporting that the intervention was mostly acceptability (only minor issues unacceptable and these could be fixed)	Four or more staff reporting major areas of unacceptability, or many staff reporting numerous minor issues that need to be addressed before proceeding	Half or more staff reporting that the intervention is unacceptable in one or more major, fundamental ways	

Page 47 of 50

31	Acceptability of the intervention from a customer perspective – interviews	Customer interviews	80% or more of customers reporting positive views about acceptability of the intervention from the perspective of a customer accessing the normal pharmacy services.	50% or more of customers reporting positive views about acceptability of the intervention from the perspective of a customer accessing the normal pharmacy services.	30% or more of customers reporting positive views about acceptability of the intervention from the perspective of a customer accessing the normal pharmacy services.	
32	Feasibility of each of the components of the intervention and as a whole - Consideration will be given to: any unintended or adverse consequences, the degree of local adaptation that would be required, who would deliver the training, who would deliver the mentoring, factors that facilitate/hinder the intervention, and its overall benefits and limitations of the intervention.	Feasibility workshop	Overall favourable opinion from all participants at the feasibility workshop (with due consideration of all feasibility data presented at the workshop), or reporting of only minor issues that could be fixed	One quarter or more of participants reporting major areas of unacceptability, or many participants reporting numerous minor issues that need to be addressed before proceeding, at the feasibility workshop (with due consideration of all feasibility data presented at the workshop)	One half or more of participants reporting that the intervention is unacceptable in one or more major, fundamental ways, at the feasibility workshop (with due consideration of all feasibility data presented at the workshop)	

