33	Effectiveness of dissemination and promotion of intervention		70% of more or customer survey respondents aware of the service (intervention)	50% of more or customer survey respondents aware of the service (intervention)	30% of more or customer survey respondents aware of the service (intervention)	
34	Final consideration of the feasibility of the actual intervention. Are all the components of the intervention feasible and needed? Are there any other components that should be added?	Consideration of: 2,3,4,9,10,11,12, 14,15,16,17,18, 20,21,30,32, 33 &34 By research team, PPI panel and CTU				
35	Feasibility of a future trial – Is a trial possible?	Consideration of: 1,5,6,7,8,10,11,12, 14,15,16,17,18,19, 20,21,22,23,24,25, 26,27,28,29,30,31, 32 & 34 and questions in 35 Research team and CTU				
	What will be primary and secondary outcomes in a future cluster RCT? What are the feasible differences in primary outcome between the intervention and control groups, and the estimated intraclass correlation? Would stratification be required in the trial (type of pharmacy,					

Page 48 of 50

urban/rural location,			
socioeconomics of area,			
ethnic diversity of			
area)?			
Should sub-groups be			
considered? Is it			
feasible to randomise?			
Is it feasible to recruit			
controls?			
Power calculation and			
sample size required,			
for whole sample and			
any sub-groups.			
Possible sources of			
contamination, for			
example staff moving			
between pharmacies.			
How data would be			
analysed?			
Can quality of life,			
acceptability and			
satisfaction, and other			
health economic criteria			
be measured?			
What would be the			
requirements for future			
funding?			
	1		

 \*It is expected that should a criteria be recorded as red, this will be reviewed by the study team and adjustments made accordingly to any future design.

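### Several progression bands in Appendix 1 fail as written: red is a floor in rows 31 and 33, amber is also red in row 8, rows 26–27 mishandle the control arm, and rows 18–28 leave middle results without a colour

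*Protocol*

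**What the plan says.** Section H of the protocol presents Appendix 1 as the list of criteria for moving to a full trial, with indicative colours. Rows 34 and 35 draw on the other rows: row 33 feeds row 34, and rows 8, 18–28 and 31 feed row 35. The footnote attaches one consequence to a colour: a red criterion is reviewed by the study team and the future design is adjusted.

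- **Row 33 (awareness).** Green is "70% of more or customer survey respondents aware of the service (intervention"), amber has the same form at 50%, and red is "30% of more or customer survey respondents aware of the service (intervention").
- **Row 31 (customer acceptability).** Green is 80% or more, amber 50% or more, and red is "30% or more of customers reporting positive views about acceptability of the intervention".
- **Row 8 (training).** Green needs all 24 staff. Amber is "Staff from half of the pharmacies attended training"; red is "Failure to train anyone in a particular pharmacy".
- **Row 27 (control pharmacies).** Green is "Able to collect at least 80% of the data from all 4 intervention pharmacies". Red also refers to intervention pharmacies. Amber is blank.
- **Row 26 (business data, both arms).** The completeness thresholds, 90% for green and 50% for red, name intervention pharmacies only. Amber is blank.
- **Rows 18–25 (data completeness).** Green is a level achieved. Most lower bands are worded as failures, such as "Failure to record at least 50% of the data for at least 50% of the clients", which is amber in rows 18, 20 and 22–25 and red in row 21.
- **Row 28 (survey).** Green is 600 responses, amber 400, and red is "Completion of 300 or less full responses to community survey within the time period".

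**The concern.** A traffic-light table is useful if every possible result gets one colour and the colours run in order. Here some rows leave results without a colour, one row gives a single result two colours, and one row names the wrong arm.

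The footnote's review starts only when a criterion is recorded as red, so a poor result with no colour does not call for it. In row 33 the uncoloured zone is where the protocol expects the result to fall. In rows 26 and 27 the thresholds miss or mislabel the control arm, although the Business data section says controls are included because they will give useful data for a future trial. If the bands are settled after the results are known, they are no longer pre-specified criteria.

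**Working it through.** **The protocol's own figure on awareness.** Size of sample assumes awareness between 10% (8.3% to 11.7%) and 30% (27.4% to 32.6%). The usual interval is p ± 1.96 × √(p(1−p)/n).

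- n = 1200 (people targeted): 1.96 × √(0.10 × 0.90/1200) = 1.7 points, giving 8.3% to 11.7%; 1.96 × √(0.30 × 0.70/1200) = 2.6 points, giving 27.4% to 32.6%. Both match.
- n = 600 (responses planned): 7.6% to 12.4% and 26.3% to 33.7%.

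The stated precision thus rests on 1200 rather than 600. That is a separate matter; only the assumed range of 10% to 30% is used below.

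**Rows 31 and 33, read literally in whole percentages.**

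| Result | Row 33 | Row 31 |
|---|---|---|
| 0–29% | no colour | no colour |
| 30–49% | red | red |
| 50–69% | amber and red | amber and red |
| 70–79% | all three | amber and red |
| 80–100% | all three | all three |

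Of the 21 whole percentages from 10 to 30, the 20 from 10 to 29 have no colour in row 33. For row 31 with 24 interviews, 0.30 × 24 = 7.2, so 0 to 7 positive customers have no colour. With 16 interviews, 0.30 × 16 = 4.8, so 0 to 4 have none.

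**Row 8, eight intervention pharmacies with three staff each.**

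- Four pharmacies represented: amber is met, and 8 − 4 = 4 pharmacies have nobody trained, so red is met too.
- Five to seven represented: red only. Training staff at seven pharmacies therefore never rates better than training staff at four, and can rate worse.
- All eight represented but 8 to 23 staff trained: no colour. An example is 23 of 24.
- If amber is taken as at least half, 23 of 24 becomes amber, but the overlap with red widens to four to seven pharmacies.

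**Rows 26 and 27.** Section D gives 8 intervention and 4 control pharmacies. Row 27's title and its count of 4 fit only the controls. Row 26 puts both arms in scope, then sets completeness thresholds for one.

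**Gaps in rows 18–28.** For simplicity, use the same percentage for data and for clients (or pharmacies), and read failure as missing the stated threshold.

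| Row | No colour |
|---|---|
| 18, 20 | 50–99% |
| 19 | 30–79% |
| 21 | 50–79% |
| 22–25 | 50–79% |
| 26 | 50–89% |
| 27 | 50–79% |
| 28 | 301–399 responses (99 totals, taking amber as 400–599) |

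**The other reading of failure in rows 22–25.** If it means that the stated share is missing, then 0–20% missing is green, 21–29% has no colour, 30–49% is red, and 50% or more meets amber and red. Amber then marks a worse state than red. Row 19 uses as amber the words that rows 22–25 use as red.

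**The case against.** Appendix 1 is headed as proposed criteria, and no colour stops or starts a trial. Rows 34 and 35 work by considering the listed rows, so an uncoloured result is still seen. Row 33 reaches row 35 only through row 34. No allocation, outcome definition or estimate depends on the table. All of this stands and limits the consequence.

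Four stronger readings are tempting but not supported:

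- **That 85% positive is green, amber and red at once.** This is true only literally. Descending bands are usually read as the best band met, which removes the overlap in rows 31 and 33. It does not give a colour to results below 30%.
- **That the worst results go uncoloured throughout.** This happens only in rows 31 and 33. In rows 18–28 the worst results reach red, and the gaps lie above them.
- **That control-arm data are never assessed.** Row 27's intent can be recovered from its title and its count of 4. Row 26 is the real omission, because nothing in its thresholds points to the controls.
- **That rows 22–25 certainly leave 50–79% uncoloured.** This depends on how failure is read. The wording is defective on both readings, but in different ways.

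**Conclusion.** The point holds in this limited form. The main defects are:

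- the direction of red in rows 31 and 33, which leaves everything below 30% uncoloured, including 10% to just under 30% of planned awareness;
- the clash between amber and red in row 8;
- the control arm, mislabelled in row 27 and left out of the completeness thresholds in row 26.

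The middle gaps and the ambiguous failure wording in rows 18–28 are secondary. They still matter, because the protocol lets staff omit supplementary (Part B) data in distress or urgency, so partial completeness is foreseeable.

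This assumes that row 33's survey is the public e-survey, the only survey described, and that amber in row 28 means 400 to 599. Red is a prompt for review, so the harm is a missed or disputed review and not a wrong stop. These are thresholds that the protocol itself states, so they should be corrected there.

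**What to change.** Reword Appendix 1 before results are seen.

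- **Rows 31 and 33:** word red as less than the lower edge of amber, that is below 50%. On the best-band reading no result that now has a colour changes it. The whole planned awareness range of 10% to 30% would then be red, which the team should note when confirming the levels.
- **Row 8:** amber when every pharmacy has at least one trained person but fewer than 24 are trained; keep red for any pharmacy with nobody trained. Staff from half of the pharmacies would then be red only, which that result already meets.
- **Row 27:** replace intervention with control in both cells.
- **Row 26:** apply the completeness thresholds to intervention and control pharmacies.
- **Rows 18–28:** state each band as at least X% of data recorded for at least Y% of clients or pharmacies, with no gaps. Give rows 26 and 27 an amber band between their existing red and green cut-points.

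Some gaps can be closed at more than one cut-point: 30% or 50% in rows 19 and 22–25 (row 19 itself states only 30%), 50% or 80% in row 21, and 300 or 400 responses in row 28. In rows 18 and 20 the lower cut-points are 50% and no data at all. The study team and clinical trials unit should choose and record these boundaries in advance.

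The cost is an amendment to the appendix wording. It needs no new data and no change in sample size.

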#### Table of versions

Protocol draft version 1.0	01.09.2021	Submitted to University of Lincoln Research Ethics as sponsor on 24.09.21		
	02.11.2021	Updated after feedback from sponsor and re-submitted on 15.11.2021		
Protocol final version 1.0	14.12.2021	After final sponsor approval, submitted and approved by NHS Research Ethics (IRAS)		
Protocol version final 1.1	12.11.2022	Approved by sponsor and submitted to IRAS		

Page 50 of 50
